4.4.1.1.2 Maximum Overall Intensity

Maximum intensity is derived from the daily intensities computed as described in [Section 4.4.1.1.1](#) and is calculated as the maximum of the daily intensities over the period considered.

Note: The maximum intensity could be considered “None” (not a reaction) in the analysis despite being considered a reaction by the Investigator (eg, swelling measurement > 0 mm but < 25 mm in adults). The maximum intensity on the ongoing period is derived from the record of the maximum intensity/measurement after the end of the solicited period following the rule described above.

For those participants receiving a non-study authorized/approved COVID-19 vaccine (eg, on Day X) within the solicited collection period, the maximum intensity of solicited reactions in main safety analysis is derived on daily intensities from D01 to Day X.

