4.4 Derived Endpoints: Calculation Methods

4.4.1 Safety

The main safety analysis will include all events or reactions with time of onset before the date of receiving a non-study authorized/approved COVID-19 vaccine and including only the corresponding safety data collected before the date of receiving a non-study authorized/approved COVID-19 vaccine. The endpoints derivations for safety analysis are detailed in the following sections. Conducting main analysis with data censored by the date of receiving a non-study authorized/approved COVID-19 vaccine will only be applied to some selected endpoints. Details on the conduct of the main safety analysis for those endpoints are provided in the following subsections. Other endpoints will be analyzed as usual. Events or reactions with time of onset on or after the date of receiving a non-study authorized/approved COVID-19 vaccine will be listed separately.

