4.4.1.1.3 Presence

Presence is derived from the maximum overall intensity on the period considered:

- None: No presence
- Grade 1, Grade 2, or Grade 3: Presence
- Missing: Missing presence

Participants with at least one non-missing presence for a specific endpoint will be included in the analysis. Conversely, those without a non-missing presence will not be included in the analysis of the endpoint.

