4.4.1.1.4 Time of Onset

Time of onset is derived from the daily intensities computed as described in [Section 4.4.1.1.1](#). It corresponds to the first day with intensity of Grade 1, Grade 2, or Grade 3.

Note: If a reaction is not continuous (ie, reaction occurs over 2 separate periods of time intervened by at least 1 daily intensity, Missing or None) then the time of onset is the first day of the first occurrence. The categories for time of onset are presented in [Table 4.1](#).

Table 4.1: Categories for time of onset

Injection Site and Systemic Reactions (D01-D08)
D01-D04
D05-D08

Main safety analysis will include only those solicited reactions with time of onset before a participant received a non-study authorized/approved COVID-19 vaccine. Events or reactions with time of onset on or after the date of receiving a non-study authorized/approved COVID-19 vaccine will be listed separately.

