4.4.1.1.5 Number of Days of Occurrence

Number of days of occurrence over the period considered is derived from the daily intensities computed as described in [Section 4.4.1.1.1](#). It corresponds to the number of days with daily intensities of Grade 1, Grade 2, or Grade 3. But if a reaction is ongoing at the time of receiving an authorized/approved COVID-19 vaccine, the daily intensities on or after that point will not be considered. Number of days of occurrence on the solicited period with a specified intensity may also be derived. The categories for number of days of occurrence during the solicited period are presented in [Table 4.2](#).

The number of days of occurrence for main safety analysis will treat the date of receiving non-study authorized/approved COVID-19 vaccine as the censored date and only daily intensities that occurred before the vaccination date will be analyzed.

Table 4.2: Categories for number of days of occurrence during the solicited period

Injection Site Reactions (D01-D08)	Systemic Reactions (D01-D08)
1-3 days	1-3 days
4-7 days	4-7 days
8 days	8 days

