5.1 Statistical Methods

Safety, immunogenicity, and efficacy analysis will be undertaken including those data collected before the date of receiving an authorized/approved COVID-19 vaccine. Those data collected on or after receiving an authorized/approved COVID-19 vaccine will be listed separately.

For those participants who did not receive an authorized/approved COVID-19 vaccine outside the study, immunogenicity data collected until the last scheduled/unscheduled study visit will be used for analysis. Rules about how to handle unscheduled visit are detailed in Table 5.2. Safety data collected until the last phone contact will be used for analysis if participants did not receive an authorized/approved COVID-19 vaccine outside the study

Safety analyses will be conducted based on two populations: *i*) participants in the Full Enrollment Cohort (Cohort 1 and 2) only, and *ii*) all participants in the Full Enrollment Cohort and Sentinel Cohort, if necessary. Immunogenicity analyses and efficacy analyses will be conducted based on the combined population (Full Enrollment Cohort + Sentinel Cohort) only, in which the same

dose-level group in Sentinel Cohort and Full Enrollment Cohort will be pooled. Subgroup analyses will be performed by age-group.

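### The solicited maximum-intensity rule runs to the day of an outside COVID-19 vaccine, so that day's record can raise the grade of a reaction that began earlier

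*SAP*

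**What the plan says.** The governing text, SAP 4.4.1, limits the main safety analysis to events with onset before the outside vaccine, "including only the corresponding safety data collected before the date of receiving a non-study authorized/approved COVID-19 vaccine". It adds that this censoring applies to selected endpoints, with details in the subsections.

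The subsections on solicited reactions then set their own cuts:

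- 4.4.1.1.2 (maximum intensity): "the maximum intensity of solicited reactions in main safety analysis is derived on daily intensities from D01 to Day X", where Day X stands for the date of the outside vaccine.
- The presence rule in 4.4.1.1.3 gives no separate cut and relies on that maximum: "Presence is derived from the maximum overall intensity on the period considered".
- 4.4.1.1.4 (onset): "Main safety analysis will include only those solicited reactions with time of onset before a participant received a non-study authorized/approved COVID-19 vaccine". For a reaction that clears and returns, "then the time of onset is the first day of the first occurrence".
- 4.4.1.1.5 (days of occurrence): for a reaction ongoing at receipt, "the daily intensities on or after that point will not be considered"; and in general "only daily intensities that occurred before the vaccination date will be analyzed".

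SAP 5.1 repeats the cut for all analyses: "Those data collected on or after receiving an authorized/approved COVID-19 vaccine will be listed separately".

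**The concern.** The maximum-intensity rule and the days-of-occurrence rule work on the same daily records and are equally specific, yet they stop one day apart. Preferring the specific rule over the general one therefore does not settle the matter.

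The extra day is the one most open to contamination. Fever, chills, headache or myalgia on Day X may come from the outside vaccine. No causality step can correct this, because Protocol 10.3.1 treats solicited reactions as related to the study intervention by definition. The temperature notes following Table 10.3 name the evening as the best time to measure, so a Day X temperature may well be taken after the outside injection.

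Presence of solicited reactions is a primary safety endpoint (Protocol Table 3.1), and SAP 5.1.1.2 tabulates each reaction by onset, maximum intensity and number of days. At stake are the grade distribution in that summary and agreement between its tables.

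**Working it through.** No figure in the plan is in dispute, so the check compares the rules and applies them to examples.

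**Step 1. Rules side by side, for a participant vaccinated outside the study on Day X**

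| SAP section | Quantity | Treatment of Day X |
|---|---|---|
| 4.4.1 | Main safety analysis | Excluded |
| 4.4.1.1.2 | Solicited maximum intensity | Included, on the natural reading |
| 4.4.1.1.3 | Presence | Taken from the maximum |
| 4.4.1.1.4 | Solicited onset | Onset must precede receipt |
| 4.4.1.1.5 | Days of occurrence | Excluded |
| 4.4.1.1.6 | Overall days | Missing if ongoing at receipt within the solicited period |
| 4.4.1.1.7 | Ongoing status | Missing if receipt falls in the solicited period |
| 4.4.1.2.2, 4.4.1.2.5 | Unsolicited AE intensity and duration | Missing if the AE began earlier and runs to Day X or later |
| 5.1 | All analyses | Listed separately |

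The SAP's other day ranges (D01-D08, D01-D04) include their end day, which is why the second row is read as inclusive.

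**Step 2. Apply the rules to assumed diaries, with Day X = D06**

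- Maximum as written = highest grade over D01 to D06.
- Maximum with the cut before Day X = highest grade over D01 to D05.
- The onset filter passes if the first day at Grade 1 or above is earlier than D06.
- Grade 3 days under 4.4.1.1.5 = number of Grade 3 days over D01 to D05.

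| Assumed diary | Onset | Onset filter | Maximum as written | Maximum cut before Day X | Grade 3 days |
|---|---|---|---|---|---|
| A: Grade 1 on D02, clear D03-D05, Grade 3 on D06 | D02 | passes | Grade 3 | Grade 1 | 0 |
| B: Grade 1 on D04-D05, Grade 3 on D06 | D04 | passes | Grade 3 | Grade 1 | 0 |
| C: clear to D05, Grade 3 on D06 | D06 | fails | Grade 3 | None | 0 |

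A and B stay in the main analysis and are graded 3 because of the Day X record alone. If days are also counted by intensity, which 4.4.1.1.5 allows but does not require, the same participant has no Grade 3 day. C is removed by the onset filter, although 4.4.1.1.2 and 4.4.1.1.3 read alone would call it present.

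**Step 3. Scale of one regraded participant**

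Inputs are the planned vaccine group of 44 and its 18-49 years stratum of 20 (Protocol Table 4.3), with Clopper-Pearson 95% intervals as in SAP Section 5.

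- Group: 0/44 = 0.0% (0 to 8.0) becomes 1/44 = 2.3% (0.1 to 12.0).
- Stratum: 0/20 = 0.0% (0 to 16.8) becomes 1/20 = 5.0% (0.1 to 24.9).

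These are Grade 3 rates. In A and B the reaction was present before Day X, so the presence rate does not move.

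**The case against.** - **The onset filter.** A reader might infer that any reaction starting on Day X counts in the primary solicited endpoint. The documents do not support that: 4.4.1 and 4.4.1.1.4 exclude such reactions from the whole main safety analysis and list them. This objection stands, and it confines the problem to reactions that began before Day X.
- **Other rules.** A reader might also infer that all other safety rules stop before Day X. They do not: some set values to Missing, laboratory results (4.4.1.4) carry no such cut, and 4.4.1 restricts censoring to selected endpoints. The conflict is with 4.4.1, 4.4.1.1.5 and 5.1.
- **Wording.** The range is not expressly labelled inclusive, and 4.4.1 could be used to read it as ending before Day X. SAP 3.1, which keeps data up to the point of receipt, settles nothing. This is fair, but a programmer following 4.4.1.1.2 literally would include the day.
- **Injection-site terms.** Protocol Table 10.2 ties these to the site and limb of the study injection, so a sore other arm is not that endpoint. This stands; systemic terms are the main exposure.
- **Reach.** Enrollment required no intention to take another vaccine before D43 (Protocol 5.1). The number affected may be zero. It is still possible, since outside vaccination was allowed at any time (Protocol 4.1) and participants were unblinded and counselled about other vaccines after 27 September 2021 (SAP Section 1).
- **Lost data.** Day X may hold a genuine study reaction from before the outside injection. That is true of either convention, but the SAP has already chosen to drop Day X elsewhere.

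**Conclusion.** The inconsistency is real. On its natural reading, 4.4.1.1.2 lets a Day X record raise the maximum grade of a reaction already under way, or of one that cleared and returned. 4.4.1, 4.4.1.1.5 and 5.1 all exclude that record, and no reason for the exception is given.

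The reach is small and unknown: participants vaccinated elsewhere within D01-D08 after a study injection, with a reaction term recorded before Day X and a higher grade on it. The 2.3% is an illustration at the planned group size, not an estimate. Enrollment stopped early and SAP 5.1 pools Sentinel and Full Enrollment dose groups, so the actual denominators are not known. It should not be read as 2.3 points on a reaction rate, because presence does not change in the cases that survive the onset filter. The point is minor, but worth correcting in a primary safety summary.

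**What to change.** In SAP 4.4.1.1.2, derive the maximum from daily intensities from D01 to the day before Day X. In 4.4.1.1.3, add that presence uses the same cut. This aligns both with 4.4.1, 4.4.1.1.4, 4.4.1.1.5 and 5.1 and removes the choice now left to the programmer. Day X records would still be listed separately under 5.1.

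The cost is one phrase and one added sentence, with no new data. The downside is that a genuine study-vaccine reaction recorded on Day X before the outside injection no longer counts towards the maximum.

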4.4.1.1.3 Presence

Presence is derived from the maximum overall intensity on the period considered:

- None: No presence
- Grade 1, Grade 2, or Grade 3: Presence
- Missing: Missing presence

Participants with at least one non-missing presence for a specific endpoint will be included in the analysis. Conversely, those without a non-missing presence will not be included in the analysis of the endpoint.

4.4.1.1.4 Time of Onset

Time of onset is derived from the daily intensities computed as described in [Section 4.4.1.1.1](#). It corresponds to the first day with intensity of Grade 1, Grade 2, or Grade 3.

Note: If a reaction is not continuous (ie, reaction occurs over 2 separate periods of time intervened by at least 1 daily intensity, Missing or None) then the time of onset is the first day of the first occurrence. The categories for time of onset are presented in [Table 4.1](#).

Table 4.1: Categories for time of onset

Injection Site and Systemic Reactions (D01-D08)
D01-D04
D05-D08

Main safety analysis will include only those solicited reactions with time of onset before a participant received a non-study authorized/approved COVID-19 vaccine. Events or reactions with time of onset on or after the date of receiving a non-study authorized/approved COVID-19 vaccine will be listed separately.

4.4.1.1.5 Number of Days of Occurrence

Number of days of occurrence over the period considered is derived from the daily intensities computed as described in [Section 4.4.1.1.1](#). It corresponds to the number of days with daily intensities of Grade 1, Grade 2, or Grade 3. But if a reaction is ongoing at the time of receiving an authorized/approved COVID-19 vaccine, the daily intensities on or after that point will not be considered. Number of days of occurrence on the solicited period with a specified intensity may also be derived. The categories for number of days of occurrence during the solicited period are presented in [Table 4.2](#).

The number of days of occurrence for main safety analysis will treat the date of receiving non-study authorized/approved COVID-19 vaccine as the censored date and only daily intensities that occurred before the vaccination date will be analyzed.

Table 4.2: Categories for number of days of occurrence during the solicited period

Injection Site Reactions (D01-D08)	Systemic Reactions (D01-D08)
1-3 days	1-3 days
4-7 days	4-7 days
8 days	8 days

4.4.1.1.6 Overall Number of Days of Occurrence

If a reaction is ongoing at the end of the solicited period, then the overall number of days of occurrence is derived from the daily intensities and the stop date of the reaction after the end of the solicited period.

The overall number of days of occurrence is:

- (stop date – last vaccination date) + (number of days of occurrence within the solicited period) – length of the solicited period + 1

If the stop date is missing or incomplete (contains missing data [MD]), the overall number of days of occurrence will be considered as Missing. If a participant received a non-study authorized/approved COVID-19 vaccine within the solicited period and the solicited reaction is ongoing at the time of the receipt of the authorized/approved COVID-19 vaccine, the overall number of days of occurrence will be analyzed as Missing for main safety analysis.

The categories for overall number of days of occurrence are presented in [Table 4.3](#).

Table 4.3: Categories for overall number of days of occurrence

Injection Site Reactions (D01-D08)	Systemic Reactions (D01-D08)
1-3 days	1-3 days
4-7 days	4-7 days
8 days or more	8 days or more
Missing	Missing

4.4.1.1.7 Ongoing

Ongoing is derived from the last daily intensity of the solicited period computed as described in [Section 4.4.1.1.1](#) and the maximum intensity in the ongoing period. The Investigator’s ongoing flag is not used because the measurement would determine the ongoing status of the reaction.

- Ongoing: if the last daily intensity of the solicited period is at least Grade 1 and the maximum intensity on the ongoing period is at least Grade 1
- Not ongoing: if the last daily intensity of the solicited period is None or the maximum intensity on the ongoing period is None
- Missing: all other conditions (in this case, it is not included in the denominator of the ongoing analysis in the safety tables)

If a participant received a non-study authorized/approved COVID-19 vaccine within the solicited period, the ongoing status will be derived as “Missing”.

4.4.1.2 Unsolicited Adverse Events

Unsolicited AEs include non-serious unsolicited adverse events (AEs), immediate unsolicited AEs, serious adverse events (SAEs), adverse events of special interest (AESIs), and medically-attended adverse events (MAAEs). Analysis for unsolicited AEs only include those AEs collected within 21 days after each injection. SAEs, AESIs, and MAAEs collected out of this range will only be presented in the analysis of SAEs, AESIs, and MAAEs.

4.4.1.2.1 Presence

An observation was considered an event if it had at least a verbatim term and was not a Grade 0 intensity event.

Grade 0 events should be included in a separate listing “Unsolicited AEs not included in the safety analysis”.

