4.4.1.2.2 Intensity

Intensity for unsolicited AEs will be derived according to the following classification: None, Grade 1, Grade 2, Grade 3, or Missing.

If the unsolicited AE is measurable and its preferred term is part of the list of solicited reactions, then the measurement is derived based upon and following the same rule of the intensity scales defined in the protocol for that measurable injection site or systemic reaction.

Note: the intensity could be considered “None” (not a reaction) in the analysis despite being considered a reaction by the Investigator (eg, swelling measurement > 0 mm but < 25 mm in adults).

Intensity for the other unsolicited AEs will correspond to the value reported in the CRF.

The maximum intensity corresponds to the highest intensity for a unique term.

For those participants receiving a non-study authorized/approved COVID-19 vaccine (eg, on Day X), the maximum intensity of unsolicited AE is analyzed as following:

- If an unsolicited AE with both time of onset and stop date before Day X, then the maximum intensity for that AE will be analyzed as collected in CRF.
- If an unsolicited AE with time of onset before Day X and the corresponding stop date is on or after Day X, then the maximum intensity for that AE will be analyzed as Missing.

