4.4.1.5.8 MAAE

A MAAE is a new onset or a worsening of a condition that prompts the participant to seek unplanned medical advice at a physician’s office or Emergency Department. Physician contact made over the phone or by e-mail will be considered a physician office visit for the purpose of MAAE collection. This includes medical advice seeking during the study visit or routine medical care. This definition excludes pediatric check-ups, follow-up visits of chronic conditions with an onset prior to entry in the study and solicited reactions.

MAAEs will be analyzed during the following time periods:

- Within 21 days after each injection
- During the study (ie, all MAAEs occurred during entire the study or the cutoff date which corresponds to the date of any interim analysis)

Note: MAAEs with date of onset before first vaccination (negative time of onset) will not be included in analysis but will be listed separately.

Main safety analysis will include only those MAAEs with time of onset before a participant received a non-study authorized/approved COVID-19 vaccine, if applicable. MAAEs with time of onset on or after the date of receiving a non-study authorized/approved COVID-19 vaccine will be listed separately.

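### Read as written, the SAP's Grade 0 rule would drop a medically attended (and, by its wording, a serious) fever, erythema or swelling measured below the solicited cut-off from the MAAE and SAE tables

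*SAP*

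**What the plan says.** Three consecutive pieces of SAP 4.4.1.2 matter.

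- **Scope (4.4.1.2).** The class of unsolicited AEs is defined to contain "serious adverse events (SAEs), adverse events of special interest (AESIs), and medically-attended adverse events (MAAEs"), alongside non-serious and immediate events.
- **Presence (4.4.1.2.1).** "An observation was considered an event if it had at least a verbatim term and was not a Grade 0 intensity event". Excluded records have a destination: "Grade 0 events should be included in a separate listing “Unsolicited AEs not included in the safety analysis".
- **Intensity (4.4.1.2.2).** For an event recorded with a measurement, the wording is: "its preferred term is part of the list of solicited reactions, then the measurement is derived based upon and following the same rule". The rule meant is the protocol scale for the matching solicited reaction. A note there accepts that the analysis may class as None something the Investigator regarded as a reaction. All other unsolicited AEs keep the CRF grade.

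The cut-offs are in SAP 4.4.1.1.1: None is below 25 mm for measurable injection-site reactions and below 38.0°C for fever.

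The MAAE definition is of another kind: "A MAAE is a new onset or a worsening of a condition that prompts the participant to seek unplanned medical advice" (SAP 4.4.1.5.8; likewise protocol 10.3.1). SAEs qualify through the seriousness criteria in protocol 10.3.2. Neither definition mentions intensity. SAP 4.4.1.3 and 4.4.1.5.8 describe the during-study period as covering all such events.

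**The concern.** Presence of MAAEs and presence of SAEs and AESIs throughout the study are primary safety endpoints (protocol Table 3.1). A temperature or size cut-off designed for grading solicited reactogenicity is not part of what makes an event medically attended or serious. Applied to the whole unsolicited class, it lets a measurement decide whether a qualifying event is counted. A programmer who follows 4.4.1.2 literally would filter these events out before the MAAE and SAE tables are built, and nothing in the sections on those tables tells the programmer to put them back.

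**Working it through.** The plan states no figure to reproduce; its safety analysis is descriptive and it has no power calculation. The check is to run the SAP's rules in order on boundary values.

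**Inputs**
- Scope: SAEs, AESIs and MAAEs are unsolicited AEs (SAP 4.4.1.2).
- Grade: derived from the measurement for fever, injection-site erythema and injection-site swelling (SAP 4.4.1.2.2, cut-offs in 4.4.1.1.1; protocol 10.3.5.1.2 also uses the solicited scale).
- Presence: verbatim term present and not Grade 0 (SAP 4.4.1.2.1).
- Assumption: derived None = Grade 0.

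**Rule chain**

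| Recorded value | Derived intensity | Counted as an event? |
|---|---|---|
| Swelling 24 mm | None | No, listing only |
| Erythema 25 mm | Grade 1 | Yes |
| Temperature 37.9°C | None | No, listing only |
| Temperature 38.0°C | Grade 1 | Yes |
| Pyrexia, no temperature recorded | Missing | Yes |

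Seriousness and medical attendance enter at no step. The last row is an oddity: an event without a measurement is kept, while the same event with a sub-threshold measurement is not.

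**Do later sections switch the rule off?** SAP 4.4.1.3, 4.4.1.5.7 and 4.4.1.5.8 add exclusions of their own (onset before vaccination; onset on or after a non-study COVID-19 vaccine). They give no presence rule and no Grade 0 exemption. Their references to all SAEs or all MAAEs describe the period, and they sit awkwardly with 4.4.1.2.1. In SAP 4.4.1.5.6 the SOC/PT summary repeats a grade filter for unsolicited AEs that ended participation (at least Grade 1, or missing). The disposition and safety-overview counts in the same section have no grade condition.

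**Which events can be caught?** Solicited reactions are excluded from MAAEs by definition, and the solicited window is D01 to D08. The route is therefore mainly onset after D08. A late 20 mm injection-site swelling that prompts an unplanned clinic visit is an example: it meets the MAAE definition, is treated as related by convention (SAP 5.3.1.2), and is derived as None.

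**Size, for illustration only.** The documents give no frequency. Assume one affected participant in a planned group (protocol Table 4.3), with exact Clopper-Pearson intervals as in SAP section 5:

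- N = 44: 1/44 = 2.3% (95% CI 0.06 to 12.0) if kept; 0/44 = 0% (0 to 8.0) under the rule.
- N = 22: 1/22 = 4.5% (0.1 to 22.8) if kept; 0/22 = 0% (0 to 15.4) under the rule.

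**The case against.** The strongest points on the other side, and what stands of each:

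- **Grade 0 is not defined, and 4.4.1.2.2 says None.** This stands as a caveat. The equation is an inference, but a strong one. The protocol scale for other unsolicited AEs has only Grades 1 to 3, so None is the only class below Grade 1, and without it the presence rule would have almost nothing to act on.
- **SAEs may be outside the rule.** Protocol 8.4.4 introduces the grading scale as one for non-serious unsolicited AEs, and SAP 5.1.1.2 tabulates any SAE. Against that, protocol 10.3.5 gives every AE a grade, and SAP 4.4.1.2.2 has no seriousness limit. For SAEs the text is unclear, not settled. MAAEs can be non-serious, so this does not reach the main case.
- **The route is narrow.** This stands. Only three terms are affected and a sub-threshold measurement must be recorded. Protocol 10.3.3 asks for the diagnosis rather than the sign where possible, so many febrile visits would be coded as an illness and keep the CRF grade. A temperature of 37.9°C is also not fever under protocol Table 10.3, which makes the late swelling the cleaner example.
- **Nothing disappears.** This stands in part: the records go to a titled listing. A listing is not the endpoint count.
- **The sizes are hypothetical.** This stands. Enrollment and vaccination were stopped on September 27, 2021, so planned group sizes need not be the final denominators.

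**Conclusion.** The concern holds in a limited form and is minor. As written, and assuming that derived None is Grade 0, the SAP would leave a qualifying MAAE out of a primary safety table when the event is an unsolicited fever, injection-site erythema or injection-site swelling with a recorded value below 38.0°C or 25 mm. By wording the same applies to SAEs, though the documents conflict on whether it was meant to. Few such events are expected, and in a group of 44 each would shift the percentage by 2.3 points.

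A reader might infer more, but the documents do not support it:

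- **Loss from every table.** The disposition and safety-overview discontinuation counts in SAP 4.4.1.5.6 carry no grade condition.
- **Loss of AESIs.** No AESI in protocol Appendix 10.5 is a measurable solicited term, so the effect there is in wording only.
- **Loss mainly in the vaccine arms.** This is conceivable for injection-site terms, but neither document gives data that show a difference by arm.

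**What to change.** In SAP 4.4.1.2.1:

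- State that a derived intensity of None is what Grade 0 means.
- Limit the Grade 0 exclusion to unsolicited AEs that are non-serious and not medically attended.
- Keep all SAEs and MAAEs in their tables whatever the derived intensity, shown as below Grade 1 where the measurement falls under the cut-off.

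In SAP 4.4.1.5.6, align the SOC/PT summary of AEs that ended participation with the same rule, so that it agrees with the disposition and safety-overview counts beside it.

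The cost is one scoping sentence in the SAP and one condition in the program. No new data are needed, because the excluded records are already held for the separate listing.
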